### **13.2.1 Device Malfunctions**

#### **13.2.1.1 Failure to Expand or Deflation**

The expander will not be able to be fully inflated if:

- The expander antenna does not respond to the controller
- The controller fails to operate properly
- The valve of the CO2 reservoir fails to open
- The valve does not release the correct amount of CO2
- There is not enough CO2 in the reservoir to achieve final volume
- There is a leak in the implant or excessive permeation through the CO2 barrier

If the expander fails to expand or becomes deflated, removal and/or replacement may be necessary.

#### **13.2.1.2 Over Expansion and/or Rupture**

Over expansion of the expander may occur if:

- There is a change in altitude greater than approximately 3300 feet (1000 meters) from baseline leading to CO2 expansion
- The expander is filled beyond the tissue tolerance or patient comfort due to a device malfunction or operator error
- The valve fails and leaks or is stuck in the open position leading to a slow or rapid release of CO2

Rupture of the expander may occur if:

- The volume of the inner gas barrier increases beyond the maximum labelled volume
- The expander is damaged either by a sharp instrument or by blunt force trauma

An increase in volume could lead to pain and/or wound dehiscence (dependent on the healing stage of the surgical site). Once the labeled volume is reached, the

pressure inside the non-distensible inner gas barrier will increase if additional volume is added up to the point at which the gas barrier will rupture. The rupture will typically present as an opening in the anterior wall of the gas barrier through which CO2 will be released into the space between the inner barrier and outer silicone shell. The gas will permeate through the ventilation holes and the porous outer shell and dissipate in the surgical pocket (subcutaneous/subpectoral space) and surrounding tissue likely resulting in temporary subcutaneous emphysema. The CO2 will be absorbed by the body via diffusion from the tissue into the bloodstream and eliminated through normal gas exchange in the lungs. If wound dehiscence occurs, CO2 will be released via the separation of the wound. If necessary, the expander may be deflated with a hypodermic needle. The device may require removal and/or replacement (depending on the stage of expansion).

### **13.2.2 Unknown Risks**

As with any investigational device, there may be risks associated with the use of the AeroForm System that are unknown. Any unexpected adverse device effect should be reported to the sponsor immediately.

### **13.2.3 Mitigations**

AirXpanders has designed, manufactured and thoroughly tested the AeroForm System to minimize the potential complications associated with its use. This study protocol has been designed to protect the safety of the participants.

A thorough biocompatibility study was performed on all materials used in the implant that are, or could come into patient contact. Additionally AirXpanders corporate quality control systems enforce that no unintended materials are used in the manufacture of the device.

#### **13.2.3.1 Mitigations to prevent under expansion**

The electronics and communication between the reservoir valve and the controller have been tested extensively as part of the quality assurance process, as well as during bench, animal and human studies. A replacement dosage controller can be provided and bonded with the implant if the expander stops communicating with the dosage controller or the dosage controller fails to operate. The CO2 reservoir valve had been tested extensively and the reservoir is filled with a sufficient

amount of compressed CO2 to inflate the tissue expander to the labelled volume and account for expected loss due to permeation. The inner gas barrier of the expander was specifically designed to minimize the loss of CO2. The seals of the expander have been reinforced and tested to minimize the chance of leaks.

Once the desired volume is reached, if more than expected loss of volume occurs, intermittent dosing (up to 25% of the labelled volume every two weeks) using Physician Fill Mode can be done to maintain the volume of the expander.

### **13.2.3.2 Mitigations to prevent over expansion**

Once the CO2 is released into the implant, it may expand if there is a significant change in altitude. This is due to the fact that CO2 expands at higher altitudes such as during air travel. The instructions for use and device labelling contain warnings and precautions for patients planning air and mountain travel. Subjects will be required to inform their physician prior to travel and discontinue dosing for a period of at least two weeks prior to travel until their return. Care should be taken not to over fill the expander beyond tissue tolerance or patient comfort since there is no way to remove CO2.

The possibility of over filling the expander is reduced through the programmed limits of a maximum daily dose of 30cc and the interval lock out period of 3 hours. Only the investigator may add volume above these limits with the use of the Physician Master Key. The limits are intended as a patient safety feature only and are not meant to be prescriptive. The physician should exercise his/her clinical judgement to fill the expander to the desired volume according to tissue tolerance and subject comfort as noted in the Instructions For Use (IFU).

The AeroForm System has been designed and tested to address potential failures of the device that may lead to over expansion. The reservoir valve is manufactured with a non-reactive material and has been designed to fail in the closed position, thus minimizing the risk of over expansion.

### **13.2.3.3 Mitigations to prevent device rupture**

As noted above, the AeroForm System has been designed to mitigate against over-expansion which may lead to excessive pressure and potential device

rupture. Labeling and training are in place to take precautions when traveling to higher altitudes or over-filling the expander. The valve is designed to fail in the closed position minimizing the possibility of a rapid release of CO2. Injury by blunt trauma or sharp objects may result in damage to the expander, resulting in rupture which may occur with any implant. In the event of a sudden rupture of the AeroForm expander, an accumulation of CO2 under the skin (subcutaneous emphysema) could occur. CO2 is a natural product of cellular activity and is highly soluble in tissue and was chosen specifically because of its demonstrated safety when used in the body for other medical purposes. Any risks associated with tissue contact with the CO2 and the inner components of the device are negligible as both are composed of common materials used for medical purposes and are sterilized.

Rupture of the device will disable the device and will require immediate medical attention and removal of the expander.

#### **13.2.4 Protection of Study Subjects**

AirXpanders has incorporated several procedures into the investigational plan and system labelling to protect study patients from any potential adverse device effects. There are stringent inclusion/exclusion criteria in the investigational protocol that will exclude any study subject who may be at increased risk of complications. The investigational protocol requires routine office visits to assure that any acute adverse effects are detected in a timely manner and proper medical treatment can be initiated. Subjects will be instructed to call their doctor immediately if they encounter any problems with the device or experience signs of complications. The Instructions for Use (IFU) describes the proper technique for the implantation procedure and expansion process in detail and training will be provided to both Investigators and study subjects on the proper use of the device. Device Training, Investigator and Patient Reference Cards along with Patient Home Instructions are provided to reinforce this training. Only Investigators who are experienced and skilled in using breast tissue expansion devices for breast reconstruction and who are trained to the protocol and the AeroForm Tissue Expander System will be selected for participation in the study.

### **13.2.5 Human Factors Considerations**

AirXpanders has designed this device with consideration of human factors to minimize misuse of this device. Features incorporated into the device include software controls such as limiting the dosing to 10cc, 3 hour lock out intervals for repeat dosing and a maximum daily dose of three doses or 30cc. A Physician Master Key is required to dose beyond the pre-set maximum dose and dosing intervals. Labeling mitigations include Instructions for Use (IFU), Physician and Patient Reference Cards and Patient Home Instructions. Physician and patient training materials are provided prior to use of the device. Subjects will be given a Patient ID card with information for 24 hour emergency contact in the event of any device problems.

### **13.2.6 Contraindications**

The AeroForm Tissue Expander is contraindicated when:

- Tissue at the intended expansion site is determined unsuitable by the physician. To a varying degree, radiation damage, ulceration, compromised vascularity, history of compromised wound healing, infection or scar deformity may affect tissue suitability.
- There is residual gross tumor at the intended expansion site.
- There is a pre-existing physiological condition, determined by the physician, which pose a high risk of surgical or postoperative complications. To a varying degree, sensitive overlying or underlying anatomy, obesity, smoking, diabetes, autoimmune disease, hypertension, chronic lung or severe cardiovascular disease, or osteogenesis imperfecta may affect patient suitability for surgery.
- The patient has another electronic implant (e.g., pacemaker, defibrillator, or neurostimulator device)

### **13.2.7 Warnings**

#### ***Radiation Therapy***

Functional testing of the AeroForm Tissue Expander at radiation levels exceeding standard clinical practice has been performed, demonstrating no degradation in functionality. However, AirXpanders does not provide recommendations regarding the use of radiation therapy. As with any implant, the decision to use radiation

therapy should be made with the consultation of the radiation oncologist using standard radiation treatment planning.

If radiation therapy is planned, the risks of radiation therapy and alternative treatment options should be discussed with the patient. In the event that radiation therapy is administered, there should be no active expansion during radiation therapy.

### ***Overfilling***

The reservoir inside the AeroForm Tissue Expander releases a controlled amount of CO2 when the button on the hand-held controller is activated. AirXpanders recommends that the physician and the patient expand gradually. Expansion progress should be assessed by the physician based on tissue laxity, perfusion and firmness of the expander.

Note that the AeroForm Tissue Expander has a non-distensible inner liner which cannot be inflated beyond the labeled volume. Dosing beyond the labeled volume or too rapid tissue expansion may lead to increases in the relative expander pressures, possibly leading to discomfort, wound dehiscence, tissue damage or rupture of the expander. If that occurs, stop expansion immediately.

### ***Altitude Change***

Patients with an implanted tissue expander considering travel to a higher altitude should consult with their physician prior to their travel. They should be instructed to discontinue dosing for at least two weeks prior to their travel and resume dosing after their travel is complete.

An increase in altitude will lead to an increase in the expander volume and the relative internal pressure, which may cause discomfort, wound dehiscence, or damage to the expander. The volume increase will be reversed upon descent.

### ***MRI***

Do not undergo diagnostic testing with Magnetic Resonance Imaging (MRI) with the AeroForm Tissue Expander in place. MRI equipment can cause movement of the expander and result in patient injury, or expander displacement requiring revision surgery. In addition, the metal CO2 reservoir could interfere with MRI detection capabilities.

### ***Infection***

Patients who present with any active infection may need to be treated and the infection resolved before placement of the expander. Do not expose the expander to contaminants that could increase the risk of infection. Patients who present with active infection, wound dehiscence, tissue erosion, ischemia, or necrosis run an increased risk of periprosthetic infection.

***Temporary Device***

The AeroForm Tissue Expander is a temporary device intended for up to six months of implantation, and is not to be used for permanent implantation. Expanders should be removed once adequate tissue has developed. The total expansion period will vary depending on patient tolerance, tissue tolerance, and planned permanent implant size.

**13.2.8 Precautions*****Surgical Planning***

The physician should follow proper surgical procedures to minimize the occurrence of adverse reactions. A qualified physician must carefully evaluate patient suitability for expansion and desired physical outcome, expander dimensions, incision placement, pocket dissection, expander filling, and final flap dimensions using current, accepted techniques and individual experience.

***Contamination at Surgery***

To avoid contamination, aseptic technique is essential. Do not expose the expander to lint, talc, sponge, towel, and other contaminants. Contamination at the time of surgery increases the risk of periprosthetic infection which could require premature explantation of the expander.

***Damage During Surgery***

Take extreme care to avoid damage to the expander during surgery; for example:

- Excessive manipulation by forcing the expander through too small an access incision or into a small surgical pocket.
- Sharp surgical instruments, such as scalpels and needles used during the initial surgery, or hematoma/fluid evacuation. During surgery, have a sterile back-up expander readily available in case damage occurs. Products must be carefully inspected for leaks or nicks prior to use. Do not attempt to repair damaged products.

***Hemostasis and Avoiding Fluid Accumulation***

Minimize post-operative hematoma and seroma by meticulous attention to hemostasis during surgery, and possibly by postoperative use of closed drains.

Persistent, excessive bleeding must be controlled before the expander is placed. The expander may be filled to tissue tolerance at the time of surgery to help minimize serous fluid accumulation in the surrounding pocket. Any postoperative evacuation of hematoma or other fluid accumulation must be carefully conducted to avoid introduction of contaminants or damage to the expander from needles or other sharp instruments.

### ***Physician Expansion***

- DO NOT over inflate the expander, as there is no method to remove volume. For patient safety, the expander has a default maximum dose of 30cc per day. However, actual volume delivery should be guided by patient comfort and wound status.
- Excessive pressure from over expansion can lead to discomfort, wound dehiscence, tissue damage or rupture of the expander. In an emergency, the device can be deflated with a standard hypodermic needle.
- DO NOT give the Physician Master Key to the patient at any time. It is to be used exclusively by the physician to administer doses during patient office visits when therapeutically appropriate.
- If the patient has bilateral implanted expanders, she should be instructed to expand one at a time, using the controller labeled for that expander. She should not attempt to expand both expanders simultaneously using both controllers.
- During dosing, if the expander appears to be filling excessively with accompanying patient pain and/or discomfort, remove the controller from the proximity of the expander. Contact AirXpanders for technical support.

### ***Electromagnetic Interference***

The ability to establish communication between the AeroForm Tissue Expander and the Dosage Controller may be impaired by electromagnetic interference from other RF wireless devices operating nearby. Interference from other RF wireless devices may be resolved by simply moving away from the other RF wireless device.

Subjects who work in areas of high radiation, magnetic or electrical fields should discuss this with their physician prior to implantation.

### ***Over-expansion/Rupture***

- Over-expansion of the expander due to device malfunction or excessive filling by the physician, can lead to extreme pain and/or wound dehiscence or may compromise the tissue integrity and require device deflation. If the subject experiences severe discomfort due to over inflation, the tissue integrity should be assessed and the subject should be treated as necessary. The expander can be deflated with a small gauge needle however; this will permanently disable the expander necessitating removal.
- The expander could rupture if the pressure inside becomes excessive due to over expansion, a rapid release of CO2 into the expander, a significant change in altitude, or sharp or blunt force injury to the chest. Damaged, leaking, or broken expanders cannot be repaired and may require replacement surgery.

### ***No-expansion/Under-expansion***

- Under-expansion of the expander due to device malfunction or excessive permeation of CO2 through the inner liner could occur. Advise patients that the expanders may deflate, and require replacement surgery.

## **13.2.9 Other Considerations**

### **Chemotherapy**

During the course of the study, some subjects may have to undergo adjuvant chemotherapy treatment. This may delay the explant of the expander to allow for the immune system to recover prior to surgery. In the event of a delayed exchange due to chemotherapy, the subject should continue to be followed per the study protocol. If the subject is unable to maintain the study schedule due to chemotherapy, this should be documented and the sponsor should be notified.

## **14 Adverse Events**

During the course of the study, adverse event data will be collected according to the definitions below:

### **14.1 Adverse Event (AE)**

An adverse event is defined as any untoward medical occurrence in a subject, regardless of whether the event is related to the device. All adverse events occurring during the subject's participation from the time of implant to the time of explant of the expander(s) will be recorded on the AE Case Report Form. Data collected will include a description of the event, onset date, management or treatment/intervention required, outcome, and resolution date (or whether the AE is ongoing). Subjects with adverse events that are ongoing should be followed until resolution of a serious AE and/or if they may be device related. All AEs will be reviewed and assessed by the investigator for severity (Table 2) and causal relationship to the device (Table 3). The investigator will also determine whether the AE meets the definition of serious as described in Section 14.2.

The investigator will use the following definitions to rate the severity of each AE:

**Table 2 Adverse Event Severity Rating**

Severity	Description
Mild	
 
• Awareness of a sign or symptom that does not interfere with the subject's usual activity or is transient, resolved without treatment and
 
• no sequelae
 

Moderate	
 
• Interferes with the subject's usual activity and/or
 
• requires symptomatic treatment
 

Severe	
 
• Symptom(s) causing severe discomfort and
 
• significant impact on the subject's usual activity and
 
• requires treatment
 

**Note: Adverse events that are rated as severe are not the same as serious adverse events. For example a subject may have severe pain may require treatment but not lead to a 'serious' event as defined below.**

## 14.2 Serious Adverse Event (SAE)

Any untoward medical occurrence in a subject, regardless of whether the event is related to the device that:

- a. results in death;
- b. results in a life threatening illness or injury;
- c. results in a permanent impairment of a body structure or body function;
- d. requires in-patient hospitalization or prolongation of existing hospitalization
- e. results in medical or surgical intervention to prevent permanent impairment to body structure or function;
- f. results in fetal distress, fetal death, or a congenital abnormality/birth defect.

## 14.3 Device Related Adverse Event

Any sign, symptom, or disease in a study subject that occurs during the course of a clinical study that is determined by the investigator to have a causal relationship or possible causal relationship with the investigational device.

**Table 3 Adverse Event Device Relationship**

Relationship	Description
Not Related	
 
• Not associated with the device
 
• due to an underlying or concurrent illness or effect of another device or drug
 

Unlikely	
 
• Little or no temporal relationship to the study device and/or
 
• a more likely alternative etiology exists
 

Possible	
 
• Temporal sequence between device application and event is such that the relationship is not unlikely or
 
• subject's condition or concomitant therapy could have caused the AE
 

Probable	
 
• Temporal sequence is relevant or
 
• Event abates upon device removal or
 
• event cannot be reasonable explained by the subject's condition
 

Highly Probable	
 
• temporal sequence is relevant and
 
• event abates upon device removal or
 
• reappearance of the event on repeat device application
 

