### **4.1 Primary Outcome Measure**

The performance of the device will be evaluated by:

Successful tissue expansion with exchange to a permanent breast implant unless exchange is precluded by a non-device related event. The primary endpoint will be analyzed per breast. Breasts in which the expander is removed and/or replaced due to a device related adverse event or a device malfunction will be counted as failures.

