## 14.6 Reporting of Adverse Events

For the purposes of this study, adverse events will be categorized based on their relationship to the device. The Investigator at each site is responsible for monitoring the safety of the subjects enrolled at that site and for determination of the causal relationship of all adverse events to the device. All adverse events determined by the investigator to be unanticipated, serious and/or possibly, probably or highly probably related to the device must be reported to the sponsor within 24 hours after the investigator first learns of the event and to the reviewing IRB per their written policy.

An investigator shall submit to the sponsor and to the reviewing IRB a report of any unanticipated non-serious adverse device event occurring during the investigation as soon as possible, but in no event later than 10 working days after the investigator first learns of the effect.

The Sponsor is responsible for the ongoing safety evaluation of the investigational product. The Sponsor shall be responsible for immediate adjudication of all reported serious and/or device related adverse events to determine whether the event is reportable under federal regulations. The sponsor will select a safety committee comprised of at least one physician who is neither an investigator in the study or employed by the sponsor to adjudicate all adverse events to determine if the event is related to the investigational device.

The Sponsor will promptly, within 10 working days after the sponsor first receives notice of the effect, notify all participating investigators and regulatory authorities, as appropriate, of findings that could affect adversely the safety of subjects, impact the conduct of the study or alter the IRB's approval opinion to continue the study.

If the Sponsor determines that an unanticipated adverse device effect presents an unreasonable risk to subjects, the Sponsor shall terminate all investigations or parts of investigations presenting that risk as soon as possible.

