## 14.8 Device Failures

Device Failures are defined as a malfunction of the device which leads device removal and/or replacement. Device malfunctions that occur but do not lead to an adverse event or removal and/or replacement will be reported as malfunctions but not be counted as failures. The table below lists potential device malfunctions. In the event of an adverse event requiring replacement of the AeroForm expander, this will be considered a treatment failure and the patient and surgeon will have the option of replacing the AeroForm with a replacement AeroForm expander or a standard saline expander.

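### For removals driven by an adverse event, Table 3's relatedness grades overlap at the cut that decides primary failure, the relatedness call to be analysed is not named, and 14.8 needs reconciling with 4.1

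*Combined protocol and SAP*

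**What the plan says.** **Failure rule.** Section 4.1 is analysed per breast. Breasts whose expander is "removed and/or replaced due to a device related adverse event or a device malfunction will be counted as failures". A non-device-related event that prevents exchange is excepted.

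**What counts as device related.** Section 14.3 covers events "determined by the investigator to have a causal relationship or possible causal relationship with the investigational device", and 14.4 uses the same test for serious events. Section 14.6 groups the top three grades for expedited reporting: events "possibly, probably or highly probably related to the device must be reported to the sponsor within 24 hours".

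**The grades.** In Table 3, *Unlikely* has two limbs joined by and/or, the second being "a more likely alternative etiology exists". *Possible* has two limbs joined by or: a temporal sequence that makes the relationship not unlikely, or that the subject's "condition or concomitant therapy could have caused the AE". *Probable* has three limbs joined by or: relevant timing; "Event abates upon device removal"; or no reasonable explanation in the subject's condition. *Not Related* includes events due to illness or to another drug or device.

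**Who decides.** Sections 14.1, 14.3 and 14.4 rest on the investigator. Section 14.6 also gives causality to the investigator, but adds a safety committee, with at least one physician independent of the sponsor and the investigators, "to adjudicate all adverse events to determine if the event is related to the investigational device".

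**A second failure term.** Section 14.8 states: "In the event of an adverse event requiring replacement of the AeroForm expander, this will be considered a treatment failure". It sets no relatedness condition.

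**Analysis plan.** Section 5.1 refers the analysis to the XPAND plan (CTP-0003, v 9.0), which is not among the supplied documents.

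**The concern.** The point is confined to removals and replacements driven by an adverse event. Malfunction removals are failures under 4.1 without any use of Table 3.

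Within that scope, the cut between *Unlikely* and *Possible* appears to decide whether a breast is a primary failure. It also decides whether an event enters two secondary outcomes in 4.2, device related and serious device related adverse events. If one event can satisfy the wording on both sides of the cut, the scale does not determine the outcome. In a single-arm, open-label study the choice could then fall to an assessor who knows the treatment and the result.

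The protocol expects this kind of case. Section 1.2 says that necrosis, flap failure and infection can lead to expander removal, and that chemotherapy and radiation make complications worse. Section 13.2.9 expects some subjects to receive adjuvant chemotherapy during the study.

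Separately, if treatment failure in 14.8 is meant to be a 4.1 failure, replacement for an unrelated event is a failure under one section and not under the other.

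**Working it through.** The plan gives no performance goal, power or sample-size formula, so there is no design figure to reproduce. The check sets the texts side by side and then does simple arithmetic for scale.

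**Step 1: where the cut lies.** This is inferred. Section 4.1 requires a device related event, 14.3 admits a possible causal relationship, and 14.6 groups possibly with probably and highly probably. The cut therefore falls between *Unlikely* and *Possible*.

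**Step 2: test a case.** Take a wound complication after implant that leads to removal, with chemotherapy judged the likelier cause.

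| Grade | Limb met | Enough alone? | Side of cut |
|---|---|---|---|
| *Not Related* | effect of another drug | may fit | not a failure |
| *Unlikely* | a likelier alternative cause | yes (and/or) | not a failure |
| *Possible* | concomitant therapy could be the cause | yes (or) | failure |
| *Probable* | relevant timing, or abates on removal | yes (or) | failure |

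The case can meet grades on both sides. The overlap is not confined to *Unlikely* and *Possible*: relevant timing alone reaches *Probable*.

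**Step 3: compare 4.1 with 14.8.** Take a replacement for an adverse event judged unrelated. Under 4.1 it is not a failure. Under 14.8 it is a treatment failure. No section equates or separates the two terms. Section 14.8 covers replacement only, not removal alone.

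**Step 4: scale.** Inputs are up to 60 subjects (section 6) and a 71% bilateral rate in the pivotal trial (section 1.4), assumed to carry over.

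- Breasts: 60 × 1.71 = 102.6, about 103. Cross-check from the pivotal trial's 168 expanders in 98 subjects: 60 × 168/98 = 102.9. Range: 60 (all unilateral) to 120 (all bilateral).
- Shift per reclassified breast, fixed denominator: 1/103 = 0.97 points; 1/120 = 0.83; 1/60 = 1.67.
- Section 4.1 does not say whether a breast lost to a non-device-related event is a success or is excluded. If excluded, with f other failures among 103 breasts, the shift is (102 − f)/102 − (102 − f)/103 = (102 − f)/(102 × 103). For f = 0 this is 102/10,506 = 0.97 points. For an assumed f = 10 it is 92/10,506 = 0.88 points.
- Illustration only: 3 ambiguous breasts would be 3/103 = 2.9 points.

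**Step 5: how many ambiguous removals.** The documents do not say. In the two PACE phases 7 + 33 = 40 of 40 subjects completed reconstruction (section 1.4), so the number could be near zero. Those subjects came from a single site, and completion does not rule out an interim replacement.

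**The case against.** **Table 3 does not act alone.** A reader might infer that evidence against the device automatically makes an event device related. The documents do not support that. Section 14.3 still requires a judged causal or possible causal relationship with the device, and a sensible assessor would lean on the not-unlikely wording in the first limb of *Possible*. This stands as a limit on the consequence, but the overlapping wording remains.

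**The committee may absorb disagreement.** A reader might infer that differences between sites pass straight into the result. That is not shown, because 14.6 sends all adverse events to adjudication. But the committee is given no relatedness criteria beyond Table 3, and nothing supplied makes its decision the analysed one. The XPAND analysis plan may settle this.

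**Section 14.8 may be a separate category.** A reader might infer an outright contradiction with 4.1. Section 14.8 defines device failures separately and uses a different, undefined term for these replacements, so the supportable statement is only that the two passages must be reconciled.

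**All-cause events are captured.** Section 4.2 reports all adverse events whatever their cause, and Table 4 lists unplanned reoperation, including device removal or replacement. This protects the safety description but does not settle the primary endpoint.

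**The study is for continued access.** That lowers the stakes. However, section 2 also gives confirming performance as a reason for the study, and 5.1 bases the risk-benefit assessment on the performance and safety endpoints.

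**Conclusion.** The concern holds in a limited form. For adverse-event-driven removals and replacements, Table 3 does not give mutually exclusive grades at the related/unrelated cut. The supplied documents do not say whose relatedness call is analysed, and 14.8 and 4.1 use failure language that has not been reconciled.

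The size is about 1 percentage point of success per reclassified breast (0.8 to 1.7 for 120 to 60 breasts, fixed denominator). This assumes full enrolment of 60; the central figure also assumes the pivotal trial's bilateral rate.

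Two larger readings are tempting and not supported. First, applying the 1.8 to 18% failure range in section 1.2 to 103 breasts gives roughly 2 to 19 breasts. That range is an overall retrospective failure rate, not a count of removals with ambiguous causality, so it does not measure this problem. Second, no performance goal appears in the supplied documents, so no conclusion can be shown to change.

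The point should be fixed before database lock because the remedy is cheap and prevents a choice of definition once results are known. It does not invalidate the study.

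**What to change.** 1. **Table 3.** Revise every row so that the grades are mutually exclusive. An alternative cause must not by itself qualify an event as *Possible*: require a temporal sequence that makes a device relationship not unlikely, and no more likely alternative cause. State which row governs when timing is relevant but another cause is more likely. Swapping or for and in the *Possible* row alone would not do, because the overlap between *Unlikely* and *Probable* would remain.
2. **Failure definition.** Reconcile 14.8 with 4.1 so that one definition enters the primary analysis, and report all-cause replacement separately under another name.
3. **Assessor.** Unless CTP-0003 v 9.0 already rules, state that the committee's adjudicated relatedness is used for 4.1 and 4.2, with the investigator's call as a sensitivity analysis.
4. **Bounding analysis.** Add a sensitivity analysis that counts every adverse-event-driven removal or replacement as a failure whatever its grade, including *Not Related*. Leaving out *Not Related* would miss events that fit that row as well as a higher one.

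**Cost.** The changes are wording, two sensitivity analyses on data already collected, and a check against the XPAND plan and scale. Adjudication of all adverse events is already planned, so no new data or staff are needed. There are three downsides. The analysis must wait for adjudication. The scale may differ from XPAND's, which would weaken comparison with that trial. Narrowing *Possible* also moves some events toward non-failure, so the all-cause analysis in item 4 should be reported alongside the primary result.
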